9.2 Selection of Study Population

Criteria for participation in the study are provided in Sections 9.2.1 and Exclusion Criteria 9.2.2

9.2.1 Inclusion Criteria

Individuals eligible to participate in this study must meet all the following inclusion criteria:

- 1. Willing and able to provide written informed consent after the nature of the study has been explained and before the start of any research-related procedures.
- 2. Male or female between the ages of 6 and 50 years.
- 3. Genetically confirmed diagnosis of SMA Type 3.
- 4. Able to walk independently for at least 30 meters (objectively measured at screening).
- 5. Not taking Nusinersen for the treatment of SMA (Nusinersen should be stopped at least 6 months before the screening). Salbutamol is permitted only if the dose has been stable for 6 months before screening.
- 6. Able to swallow oral medication.
- 7. Female patients of childbearing potential must have a negative pregnancy test (serum human chorionic gonadotropin [HCG] at screening); and must practice an effective, reliable contraceptive regimen during the study and for up to 30 days following discontinuation of treatment.
- 8. Ability to participate in the study based on overall health of the patient and disease prognosis, as applicable, in the opinion of the Investigator; and able to comply with all requirements of the protocol, including completion of study questionnaires.

9.2.2 Exclusion Criteria

Individuals who meet any of the following exclusion criteria are not eligible to participate in the study:

- 1. Epilepsy and currently on medication.
- 2. An electrocardiogram (ECG) within 6 months before starting treatment that shows clinically significant abnormalities, in the opinion of the Investigator.
- 3. Breastfeeding or pregnant at Screening or planning to become pregnant at any time during the study.
- 4. Surgery for scoliosis or joint contractures within the previous 6 months.
- 5. Treatment with an investigational drug (other than amifampridine) or device within 6 months before Screening or while participating in this study.
- 6. Any medical condition that, in the opinion of the Investigator, might interfere with the patient's participation in the study, poses an added risk for the patient, or confound the assessment of the patient.
- 7. History of drug allergy to any pyridine-containing substances or any amifampridine excipient(s).
- 8. Less than 3-point improvement in HFMSE from start to end of Run-in period.
- 9. Uncontrolled asthma.
- 10. Concomitant use with sultopride.
- 11. Concomitant use with medicinal products with a narrow therapeutic window.

9.2.3 Removal of Patients from Treatment or Assessment

Patients may withdraw their consent to participate in the study or to receive treatment with IP at any time without prejudice. The Investigator must withdraw from the study or from treatment with IP any patient who requests to be withdrawn. A patient's participation in the study or treatment with IP may be discontinued at any time at the discretion of the Investigator and in accordance with his or her clinical judgment.

Catalyst must be notified of all patient withdrawals from the study or from treatment with IP as soon as possible. Catalyst also reserves the right to discontinue the study at any time for

either clinical or administrative reasons and to discontinue participation by an individual Investigator or site for poor enrollment or noncompliance.

Reasons for which the Investigator or Catalyst may withdraw a patient from the study treatment include, but are not limited to, the following:

- Patient experiences a serious or intolerable AE;
- Patient requires medication prohibited by the protocol;
- Patient becomes pregnant (refer to Section 10.4 Pregnancy for details on the reporting procedures to follow in the event of pregnancy).
- Patient does not adhere to study requirements specified in the protocol;
- Patient was erroneously admitted into the study or does not meet inclusion criteria;
- Patient is lost to follow-up.

If a patient fails to return for scheduled visits, a documented effort must be made to determine the reason. If the patient cannot be reached by telephone, a certified letter should be sent to the patient requesting contact with the Investigator. This information should be recorded in the study records.

The Investigator or designee must explain to each patient, before enrollment into the study, that for evaluation of study results, the patient's protected health information obtained during the study may be shared with Catalyst, regulatory agencies, and IEC. It is the Investigator's (or designee's) responsibility to obtain written permission to use protected health information, per country-specific regulations, from each patient. If permission to use protected health information is withdrawn, it is the Investigator's responsibility to obtain a written request, to ensure that no further data will be collected from the patient and the patient will be removed from the study.

9.2.4 Patient Identification

Each patient will be assigned a unique patient identifier (2 digits for the site and 2 digits for each patient enrolled). This unique identifier will be on all CRF pages.

9.2.5 Re-screening

Re-screening of screen failures will be allowed, if re-screening is approved by the Medical Monitor. Justification of the reason for re-screening must be clearly stated in the patient's source documentation. No new consent would be required if re-screened within 30 days.

Clinical laboratory tests do not have to be repeated for 30 days, except for pregnancy test. Patients may be replaced if discontinued from the study after randomization.

9.3 Treatments

9.3.1 Treatments Administered

Catalyst or its designee will provide the study site with a supply of IP sufficient for the completion of the study.

Investigational product: Amifampridine will be provided in round, white-scored tablets and containing amifampridine phosphate formulated to be the equivalent of 10 mg amifampridine base per tablet. The product will be provided in bottles of bulk tablets to the Catalyst designee who will dispense to the site an amount for each portion of the study, in a patient-specific labeled bottle.

Placebo: A placebo equivalent will be provided as tablets indistinguishable from the amifampridine tablets. The placebo will be administered consistent with the dose regimen of amifampridine. The placebo tablets will be provided in bottles of bulk tablets to the Catalyst designee, who will dispense to the site an amount, in a patient-specific labeled bottle.

9.3.2 Identity of Investigational Product

The chemical name of amifampridine phosphate is:

- 3,4-pyridinediamine, phosphate (1:1) diamino-3,4-pyridine, phosphate salt
- 3,4-diaminopyridine phosphate

The chemical structure is provided in Figure 1.

Figure 1. Chemical Structure of Amifampridine Phosphate

9.3.2.1 Product Characteristics and Labeling

Drug product is formulated as a phosphate salt of amifampridine. Tablets were developed to provide the equivalent of 10 mg of amifampridine base for oral administration. Each tablet contains amifampridine phosphate, microcrystalline cellulose, colloidal anhydrous silica, and calcium stearate. The bottles of tablets are labeled "Amifampridine Phosphate Tablets, 10 mg." Placebo will be provided as tablets indistinguishable from amifampridine.

The tablets of amifampridine and placebo are to be dispensed by the Catalyst designee into suitably sized pharmacy containers for patient use. Each bottle provided to patients will be labeled to include the compound name (Open-label or study drug, depending on the study period), site number, patient ID number, date dispensed, storage instructions, the statement 'Caution – New Drug – Limited to investigational use', trial number, manufacturer name and address, and instructions for use. Any additional regional label requirements and translations will be included in accordance with local regulations.

9.3.2.2 Storage

At the study site, all IP must be stored under the conditions specified, 20-25° Celsius (C) (excursions between 15-30° may be allowed) and in a secure area accessible only to the pharmacist and clinical site personnel. All IP must be stored and inventoried, and the inventories must be carefully and accurately documented according to applicable national and local regulations, ICH GCP, and study procedures.

9.3.3 Directions for Administration

All doses of study treatment will be taken at home, except one of the doses on the day of the in-clinic study visits, when it will be administered by study personnel and will be administered in the clinic to facilitate timing of efficacy assessments. Test medication should be taken every day at approximately the same time, at the dose and frequency instructed by Investigator. On the day of an in-clinic study visit (Days 0, 7, 14, 21, and 28), dose administration will be the medication the patient has been taking for the previous days, but administered by the study personnel 45 minutes before the first efficacy assessment. If the patient takes the dose three times a day, the patient should be given specific instructions on dosing relative to the time of their visit to assure a dose will be given during the in-clinic visit within the required time window. All safety assessments will be performed before the dose is administered to the patient during the in-clinic visit. Efficacy assessment will be performed at standardized times relative to the dose administered in the clinic.

Assessment	Start Time After Dose (+ 10 minutes unless otherwise specified)
HFSME	45 minutes
6-minute walk test	After HFSME
Time to rise from floor	After 6-minute walk
Time to rise from chair	After rise from floor
Time to climb 4 stairs	After rise from chair
Time to walk 10 meters	After climb stairs
Quality of Life Assessment	After 10-meter walk

The dose of amifampridine will be individually determined by the Investigator, within the bounds of a total daily dose of 15 mg to 80 mg, divided into doses taken 3 to 4 times per day as prescribed by the Investigator, based on optimal neuromuscular benefit. The maximum single dose is 20 mg. Amifampridine dose will be titrated upward every 3 to 4 days, starting at 15 mg/day, at the discretion of the Investigator. Pediatric dosing guidelines are presented in Table 2.

Table 2 Pediatric Dosing Guidelines

	Ages 6 to 16 Years	Ages >16 years
Recommended starting dose	5 mg, 3 times per day (15 mg/day total)	10 mg, 3 times per day (30 mg/ day total)
Initial dose escalation	May increase dose to 10 mg, 3 times per day (30 mg/day total)	May increase dose to 10 mg, 4 times per day (40 mg/day total)
Subsequent dose escalations	May increase dose to 10 mg, 4 times per day (40 mg/day total) May continue to titrate dose to 15 mg, 4 times per day (60 mg/day total)	May titrate dose up to 20 mg, 4 times per day (80 mg/day total)
Maximum dose:	60 mg/day	80 mg/day

Patients will either visit or have telephone/video contact with the site for each dose titration and at least one in-person site evaluation at Week 3 of the Run-in period. When the Investigator determines that the patient has reached the maximal tolerable dose, the patient should demonstrate they can remain on a stable dose and frequency for at least an additional 7 days. The Open-label Run-in period may be extended if additional time is needed for dose

titration. At the end of this period, patients must show a \geq 3-point improvement in HFMSE from start of Run-in, to be eligible for randomization (Day 0).

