Safety and efficacy assessments will be made, in the site clinic, on Days 21 and 28 as detailed in the Schedule of Assessments in Table 1 and Section 12 STUDY Procedures. All unused medication and the container must be brought back to the study site at each clinic visit, including on Day 28, which represents the end of the study.

Table 1 Schedule of Events

		Run-in			Period 1		Period 2	
Study Assessment or Event ^b	Screening Days -14 to -1	Start ^a Day 1	Week 3	Last Visit Day 0 end of Run-in	Day 7 ±1 day	Day 14 ±1 day	Day 21 ±1 day	Day 28 ±1 day
Informed consent c	X							
Inclusion/Exclusion Criteria	X			X				
Randomization				X				
Medical history	X							
Complete physical exam	X			X				X
Vital signs	X		X	X	X	X	X	X
12-Lead ECG and QTc evaluation	X			X				X
Clinical laboratory tests ^d	X			X				X
Pregnancy test ^e	X			X		X		X
Dispense blinded IP f,g				X		X		
IP accountability			X	X	X	X	X	X
Able to walk 30 meters	X							
INQoL or PEDSQL				X	X	X	X	X
HFMSE	X	X		X	X	X	X	X
Six-minute walk test				X	X	X	X	X
Time to rise from floor				X	X	X	X	X
Time to rise from chair				X	X	X	X	X
Time to climb 4 stairs				X	X	X	X	X
Time to walk 10 meters				X	X	X	X	X
Adverse events/SAEs h	X	X	X	X	X	X	X	X
Concomitant medications	X	X	X	X	X	X	X	X
Patient Dosing Diary Provided		X	X	X	X	X	X	

ECG = electrocardiogram; HFSME= Hammersmith Functional Motor Scale Expanded; IP = investigational product (amifampridine or placebo); INQoL = individual quality of life; PEDSQL = pediatric quality of life inventory; SAE = serious adverse event. *Footnotes continue on next page.*

^a Titrate from starting dose of 15 mg/day, every 3 to 4 days with at least one site visit at Week 3. Last week of run-in, study drug dose and frequency must be stable before being eligible for randomization on Day 0.

^b All safety assessments (vital signs, ECGs, laboratory tests) are to be performed before the dose taken in the study clinic unless specified otherwise. All efficacy assessments will be performed at standardized times relative to the dose that must be taken in the study clinic on Days 0, 7, 14, 21, and 28 according to the efficacy assessments schedule in Section 9.7.

^c Informed consent must be obtained before any study procedures are performed.

- ^d Clinical laboratory tests include serum chemistry, hematology, and urinalysis.
- ^e Serum pregnancy tests will be obtained from female patients of childbearing potential only at Screening; urine dipstick may be used for the remainder of the study.

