12 STUDY PROCEDURES

12.1 Screening Visit

An ICF must be signed and dated by the patient and parents for patients with age < 18 years, the Investigator or designee, and witness (if required) before any study-related procedures are performed. Refer to Section 9.4 for prohibited medications.

After patients have signed an ICF, they will be screened for enrollment into the study. The study activities listed below will be performed during the 14 days that constitute the Screening visit.

- Informed Consent;
- Inclusion/Exclusion criteria;
- Demographics (sex, race, ethnic origin, age);
- Medical history, including allergy history;
- Standard resting 12-lead ECG;
- Complete physical examination including weight and height;
- Vital signs (seated position), including SBP, DBP, heart rate, respiration, and body temperature;
- Clinical laboratory tests including hematology, chemistry, and urinalysis;
- Serum pregnancy test in females of childbearing potential only;
- HFSME;
- Walk 30 meters;
- SAEs;
- Concomitant medications.

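### Protocol 9.3.3 gives two starting doses for patients over 16 (15 and 30 mg/day) and leaves unclear which daily maximum, 60 or 80 mg/day, governs at ages 6 to 16

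*Protocol*

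**What the plan says.** **Starting dose.** The text of Protocol 9.3.3 reads "Amifampridine dose will be titrated upward every 3 to 4 days, starting at 15 mg/day, at the discretion of the Investigator". The synopsis, 9.1.1 and 12.2 repeat this. Footnote a to Table 1 has "Titrate from starting dose of 15 mg/day, every 3 to 4 days with at least one site visit at Week 3", and SAP Appendix 1 carries the same footnote. None of these statements is limited by age.

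Protocol 9.3.3 then adds "Pediatric dosing guidelines are presented in Table 2". That table has one column for ages 6 to 16, starting at 15 mg/day, and one for ages over 16, where the recommended start is "10 mg, 3 times per day (30 mg/ day total".

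**Daily ceiling.** The text of 9.3.3 leaves the dose to the Investigator "within the bounds of a total daily dose of 15 mg to 80 mg", with a 20 mg limit on any single dose. The synopsis, 9.3.5 and SAP 5.3 also give 80 mg/day, again without an age qualification. For ages 6 to 16, the last escalation step in Table 2 is "May continue to titrate dose to 15 mg, 4 times per day (60 mg/day total", and its maximum-dose row gives 60 mg/day. For ages over 16 the table's maximum is 80 mg/day.

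**Ages.** The inclusion criterion is "Male or female between the ages of 6 and 50 years". The only explicit age cut-off for minors is in the consent rule of 12.1: "parents for patients with age < 18 years".

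**The concern.** A dosing section should give one instruction for each patient. Here the text and the table of the same section give two starting doses above age 16, with no rule for choosing between them. A site working from the Table 1 footnote or from 12.2 would not be sent to Table 2 at all, because neither mentions it. A site working from Table 2 would start at twice the dose.

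The ceiling is the point at which following one passage could take a child above a maximum stated in another. Titration is meant to bring each patient to the highest dose he or she tolerates, so the ceiling may well be reached in practice. Monitors are asked to check adherence to the protocol (section 13), but the wording does not tell them whether such a dose is a deviation.

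**Working it through.** The plan derives no figure here, so the check is a side-by-side reading with simple dose arithmetic (single dose × doses per day).

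**Step 1. Is Table 2 internally consistent?** Yes: 5 × 3 = 15, 10 × 3 = 30, 10 × 4 = 40, 15 × 4 = 60 and 20 × 4 = 80 mg/day. The text is consistent too: its 20 mg single-dose limit × 4 doses = 80 mg/day. The disagreement is therefore not an arithmetic slip in either place.

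**Step 2. Text against table.**

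| Item | Statements without an age limit | Table 2, ages 6 to 16 | Table 2, ages over 16 |
|---|---|---|---|
| Start (mg/day) | 15 | 15 (agrees) | 30 (conflicts) |
| Maximum (mg/day) | 80 | 60 (relation unclear) | 80 (agrees) |

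- Statements giving 15 mg/day without an age limit: synopsis, 9.1.1, Table 1 footnote a, 9.3.3 text, 12.2 and SAP Appendix 1, six in all. One place, Table 2, gives 30 mg/day.
- Statements giving 80 mg/day without an age limit: synopsis, 9.3.3 text, 9.3.5 and SAP 5.3, four in all. Table 2 gives 60 mg/day at ages 6 to 16.

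**Step 3. Size.**

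- Start above age 16: 30 / 15 = 2.0. In the 6-to-16 column, 15 to 30 mg/day is the first escalation. If that also counts as one step for older patients, the two starts are one titration step, or 3 to 4 days, apart.
- Ceiling at ages 6 to 16: 80 − 60 = 20 mg/day, and 80 / 60 = 1.33, so up to 33% above the table's maximum.

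**Step 4. Does any reading of the table's scope remove the starting-dose conflict?**

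- *The upper column runs to the inclusion limit.* It then covers ages 17 to 50 and contradicts the text for every patient over 16.
- *The table is pediatric in the under-18 sense of 12.1.* In whole years the column then covers age 17 only. A 17-year-old's recommended start is 30 mg/day, twice the 15 mg/day that the text gives an adult, and the text still gives the 17-year-old 15 mg/day.

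Neither reading removes it. Section 9.7.4 separates adult from pediatric patients for the quality-of-life forms but gives no age, so it does not settle the scope.

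**Step 5. Is there a precedence rule?** Protocol 14.8 lets the SAP prevail over the protocol, but only for the statistical analysis text. No passage ranks the dosing text against Table 2.

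**The case against.** The strongest reply concerns the ceiling. A limit of 60 mg/day lies inside bounds of 15 to 80 mg/day. The paragraph that sets those bounds ends by pointing to Table 2, which has a column for ages 6 to 16 and a maximum-dose row. A general bound followed by an age-specific maximum is ordinary drafting. Read as a whole, 9.3.3 can be taken to cap these patients at 60 mg/day. This reading is reasonable, and for that reason the ceiling is called unclear rather than contradictory. It is not the only reading: the table is presented as guidance, 9.3.5 states 80 mg/day as the maximum with no exception for age, and no passage connects the two.

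On the starting dose, the reply is that the table only recommends, the Investigator has discretion, both starts are within bounds, and every titration step involves contact with the site. All of this happens in the open-label run-in, and patients must hold a stable dose for at least 7 days before randomization. These points are correct and limit the consequence. They do not say which start applies.

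Two smaller points also stand. The six statements largely repeat one template sentence, and the SAP does not direct site dosing, so the count shows how far the wording has spread and is not independent evidence. At ages 6 to 16 the text and table agree on the start, so the direct conflict does not touch that group.

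**Conclusion.** The point holds. Above age 16 the protocol gives two starting doses, 15 and 30 mg/day, and no rule for choosing between them. This is true whether the table's upper column means age 17 only or ages 17 to 50. The documents do not state that scope, so the number of patients affected cannot be given; the planned total is about 12.

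At ages 6 to 16 the ceiling is ambiguous. A patient could be dosed up to 20 mg/day (33%) above Table 2's maximum while complying with four other statements. This part is weaker, because the table can be read as an age-specific limit.

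The starting-dose problem is an ambiguous safety instruction and not an out-of-range dose. It is not a threat to the treatment comparison. It should still be corrected, because it is a dosing instruction in a trial that enrols children from age 6 and the remedy is only wording.

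**What to change.** The sponsor must reconcile the passages so that each age band has one starting dose and one daily ceiling. Which values are right is for the sponsor's clinical team, and none is proposed here. The amendment should:

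- state whether the text or Table 2 governs;
- retitle Table 2 to match the ages it covers, and define the upper end of its second column;
- say explicitly how the table's maximum for ages 6 to 16 relates to the general bounds;
- carry the same wording through the synopsis, 9.1.1, Table 1 footnote a, 9.3.3, 9.3.5, 12.2, SAP 5.3 and SAP Appendix 1.

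The cost is wording in a protocol amendment and in two places in the SAP. It adds no visits, staff or patients.

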9.3.4 Method of Assigning Patients to Treatment Groups

Patients will be randomized on the last day of the open-label run-in period (Day 0), in a 1:1 ratio, to 1 of 2 treatment sequences (amifampridine for Period 1 and placebo for Period 2 or placebo for Period 1 and amifampridine for Period 2. IP will be administered under double-blind conditions. Randomized patients who discontinue after initiation of treatment may be replaced.

The randomization code will be provided to the unblinded Catalyst designee. Details will be included in the Pharmacy Manual.

9.3.5 Selection of Doses Used in the Study

Amifampridine is given in 3 or 4 divided doses, with no single dose >20 mg and the maximum daily dose of 80 mg. Safety of a single maximum dose of 20 mg is based on completed animal and *in vitro* pharmacology, PK, and toxicology studies. Previous studies with amifampridine in this dose range have shown clinical benefit in other neurologic disorders (LEMS, MG).

9.3.6 Blinding

This is a double-blind, treatment cross-over study where both the patient and Investigator will be blinded to treatment assignment.

9.3.7 Treatment Compliance

Patients will be instructed to complete a daily Dosing Diary of study medication taken and bring the Diary, all IP containers, and remaining test medication at each study visit. Patient compliance with the dosing regimen will be assessed by reconciliation of the used and unused IP. The quantity dispensed, returned, used, lost, etc., must be recorded on the medication dispensing log provided for the study.

